9.1 Antibody Assays

Serum processed from study blood draws will be tested for biomarkers of allergen immunotherapy, such as cockroach-specific IgE and IgG4 antibodies to cockroach component allergens. These include, but may not be limited to, Bla g 1, Bla g 2, Bla g 4, Bla g 5 and Per a 7.

Serum from these blood draws will also be used to measure in-vitro cockroach antigen binding to B-cells.

9.2 Cellular Assays

Peripheral blood mononuclear cells (PBMCs) will be separated from study blood draws and used to measure the magnitude and phenotype of the CR-specific T cell response to CR immunotherapy.

9.3 Gene Expression

Blood drawn at each study blood draw will be used to extract RNA samples for whole transcriptome RNA sequencing to identify the changes in PBMC gene expression response to CR stimulation over time and compare those changes between the treated group and the untreated group. Significant differences will allow the identification of mechanisms of immune tolerance in CR SCIT.

Nasal lavage samples collected before and after each NAC will be used to compare gene expression by RNA-sequencing in nasal lavage samples pre-CR NAC with samples post-CR NAC. Samples collected at 12 months will be used to identify the changes in nasal lavage gene expression in response to CR immunotherapy between the treated group and the untreated group.

10 Biospecimen Storage

Unused samples of biological specimens collected during the course of the study will be stored (described in the Protocol ICAC-28 MOP) for future use for tests that may or may not be planned. These tests may or may not be related to the study of asthma and allergy and may include genetic studies such as DNA. Participants will be asked to give permission for long-term storage and future use during the consent process. With the participant's approval and as approved by the central IRB, de-identified biological samples will be stored indefinitely at the DAIT NIAID central repository (Eminent Services Corporation, Frederick, MD).

11 Criteria for Participant and Study Completion and Premature Study Termination

11.1 Participant Completion

Participants are considered to have completed the study once they have completed the final visit (12-month Visit).

11.2 Participant Stopping Rules and Withdrawal Criteria

11.2.1 Discontinuation of Study Therapy

Study therapy may be prematurely discontinued for any participant for any of the following reasons:

1. SAE related to investigational agent.
2. Systemic reaction grade 3 or 4 (see Table 12.3.1.1c, WAO Systemic Reaction Grading System).
3. Failure to reach the minimum maintenance dose in a forty-week period (See Appendix B: Study Restrictions Due to COVID-19).
4. Development of any serious medical illness whose natural history, sequela, or treatment would be worsened or impaired by continuation in the protocol.
5. The participant has a need to start immunotherapy or any chronic immunosuppressive medications.
6. The participant has a need for a dose of greater than 500 mcg of fluticasone per day, or the equivalent of another inhaled corticosteroid, to maintain asthma control for greater than 6 months.

11.2.2 Discontinuation of Study Participation

Participants may additionally be prematurely terminated from the study for the following reasons:

1. Pregnancy
2. The participant elects to withdraw consent from all future study activities, including follow-up.
3. The participant is "lost to follow-up" as defined in the Protocol ICAC-28 MOP.
4. The participant dies.
5. The Investigator no longer believes participation is in the best interest of the participant.
6. The participant has a need for > 3 bursts of systemic corticosteroids for asthma exacerbations during the treatment period OR has a need for > 2 bursts of systemic corticosteroids for asthma

exacerbations within 6 months during the treatment period. If prescribed by an ICAC study clinician, a burst is defined as a course for prednisone, prednisolone, or methylprednisolone will be 2 mg/kg/day as a single daily dose for 4 days with a maximum dose of 60 mg per day. The course for dexamethasone will be 0.3 to 0.6 mg/kg/day as a single daily dose for 2 days with a maximum dose of 16 mg per day. If a corticosteroid burst for the treatment of an asthma exacerbation is prescribed by a non-ICAC clinician, it will be counted regardless of dose.

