5. ANALYSIS SAMPLES

[ICH E3: 11.4.2.6](#); [ICH E9: 5.2](#)

The following groups of participants will define samples for endpoint analysis:

- **Modified Intent-to-treat (ITT) sample:** All participants who are randomized, received at least one dose of study treatment, and receive at least one dose during the 12-month NAC. Participants will be analyzed according to the treatment arm to which they were randomized, regardless of the medication they actually received.
- **Safety sample:** All participants who sign consent and undergo study procedures at Screening. Participants will be analyzed according to the medication they actually received, regardless of the treatment arm to which they were randomized. Non-treatment-emergent adverse events (e.g., any adverse event that occurs before the first injection) will be summarized in all participants who are enrolled, while treatment-emergent adverse events (e.g., any adverse event that occurs on or after the first injection) will be summarized in the safety sample.
- **Per-protocol (PP) sample:** All participants who are randomized, are escalated to at least 0.4 mL of the 1:10 maintenance dose, and receive at least 3 doses of maintenance SCIT/placebo.

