6. STUDY SUBJECTS

6.1. Disposition of Subjects

[ICH E3: 10.1](#)

The disposition of all enrolled subjects will be summarized in tables and listed. The following disposition information will be summarized:

- The number of participants screened.
- Among screened participants:
 - The number and percentage of participants who failed Screening, including those that attended the Screening visit but did not meet the inclusion/exclusion criteria.
 - The number and percentage of participants in the mITT sample.
 - The number and percentage of participants in the safety sample.
 - The number and percentage of participants in the PP sample.
- Among participants in the mITT sample and grouped by treatment arm:
 - The number and percentage of participants in the safety sample.
 - The number and percentage of participants in the PP sample.

National Institute of Allergy and Infectious Diseases
{Statistical Analysis Plan - Protocol #}

- The number and percentage of participants who completed the 12 month NAC.
- The number and percentage of participants who withdrew during the study due to:
 - Withdrawal by participant
 - Lost to follow-up
 - Death
 - Pregnancy
 - Physician decision
 - Participant experienced an anaphylactic reaction to study drug injection
 - Participant was diagnosed with an exclusionary malignancy
 - Participant acquired an opportunistic infection
 - Non-compliance with the study protocol
 - Participant refused protocol-mandated procedure at the Screening of Treatment Initiation Visit
 - Adverse Event
 - Other

A data listing of subject disposition will be provided for the mITT population.

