8.1.3. Missing Data

The primary method of handling missing efficacy data will be the use of complete case analysis for the primary analyses. Indeed, participants with missing data for the 12 months NAC will not be included in the ANCOVA with factors for arm and site and the respective baseline TNSS as a covariate.

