8.2. Primary Endpoint

[ICH E9: 2.2.2-2.2.7](#)

Variable (Endpoint): Change in mean TNSS after 12 months of treatment with cockroach SCIT.

Population: Of all subjects defined by the study inclusion / exclusion criteria, the analysis population will include subjects who are in the modified ITT and per protocol populations.

Intercurrent events: All intercurrent events will be handled following hypothetical strategy (imputation). Missing data of this nature, as well as missing data due to withdrawal, will be multiple imputed as described above in section 7.1.3.

[figure not shown]
Population-level summary: Difference between treatment groups, Cockroach SCIT vs Placebo, in the change in mean TNSS after 12 months of treatment between the placebo and treatment arm.

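### SAP 6.1 counts withdrawals by arm only among children who reached the 12-month nasal challenge, so anyone who left earlier is missing from the table by definition

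*Protocol*

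**What the plan says.** **Leaving the study.** Protocol 11.2.1 lists reasons to stop injections. Under 6.7 and 11.4, those children are asked to stay in follow-up. Protocol 11.2.2 is a separate list that ends participation: "Participants may additionally be prematurely terminated from the study for the following reasons". Item 6 reads "The participant has a need for > 3 bursts of systemic corticosteroids for asthma exacerbations during the treatment period", with an alternative trigger of more than two bursts within six months. After such an exit, Protocol 8.9 offers an Early Termination Visit with no NAC among its listed contents. Further contact is only for pregnancy or SAE outcomes. Appendix A of the protocol agrees.

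**Who is analysed.** SAP 5 admits a child to mITT only if the child was randomised, had a study injection, and went on to "receive at least one dose during the 12-month NAC". SAP 8.1.3 makes the primary analysis complete-case: "participants with missing data for the 12 months NAC will not be included in the ANCOVA". SAP 8.2 says instead that "missing data due to withdrawal, will be multiple imputed". That conflict is a separate matter. Under either rule the mITT definition leaves out a child who never reached the 12-month NAC.

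**What is tabulated.** SAP 6.1 opens by saying that disposition will be tabulated and listed for everyone enrolled. Its itemised by-arm block is headed "Among participants in the mITT sample and grouped by treatment arm" and contains "The number and percentage of participants who withdrew during the study due to", followed by a list of reasons. The section ends: "A data listing of subject disposition will be provided for the mITT population".

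**The concern.** A withdrawal table exists to show who was lost, from which arm and why. Here the denominator is the set of children who were not lost before the endpoint visit. The counts that would let a reader judge informative or unequal loss are therefore removed before the table is built.

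Item 6 shows why this matters. Repeated steroid bursts are an asthma outcome that arises after randomisation, so treatment could influence who exits by this route. If such exits differed between arms, the complete-case comparison of mean TNSS would no longer rest on the groups as randomised, and the planned withdrawal counts would not show it.

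The reason rows also fit the protocol poorly. They name malignancy and opportunistic infection, which neither 11.2.1 nor 11.2.2 names, and they have no row for steroid bursts.

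**Working it through.** **1. The plan's own figure.** Protocol 13.6 states 83% power for a total of 54, with difference 0.88, SD 1.09 and two-sided 0.05. A two-sample t-test with n per arm has noncentrality 0.88 / (1.09 × √(2/n)). With n = 27 this is 0.88 / 0.297 = 2.97 and power is 82.9%, so the figure reproduces. At 80 in total, power is 94.6%; at 76 it is 93.5%. The plan can lose 80 − 54 = 26 children (26/80 = 32.5%) and still have its stated power. Power is not the issue.

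**2. What the table can contain.**
- In mITT: randomised, at least one injection, at least one dose at the 12-month NAC.
- Left before that NAC: no dose at it.
- Overlap of the two groups: none.

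The table can count as withdrawn only a child who had a dose at the 12-month NAC but did not finish the final visit. Protocol 8.8 and 11.1 make the 12-month visit the last one, so that window is narrow. The row for completing the 12-month NAC has the same flaw, because everyone in its denominator has already started it.

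**3. Illustration (not a forecast).** Take 80 children randomised 40/40, with 26 leaving before the NAC.

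| Split of losses | True loss by arm | Early withdrawals in SAP 6.1 table |
|---|---|---|
| 13 and 13 | 13/40 = 32.5% in each | 0 of 27 and 0 of 27 |
| 26 and 0 | 26/40 = 65% and 0% | 0 of 14 and 0 of 40 |

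The withdrawal and reason rows are the same in both cases. Only the column totals differ.

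**4. How many exits item 6 could add.** The documents give no burst rate, so these rates are assumed. In a simulation of 600,000 children per scenario, each child has a stable yearly rate, either common to all or gamma-distributed with shape 2, 1 or 0.5. Children enter only if they pass the steroid-course limits in Protocol 4.3. Exit occurs at the fourth burst, or at the third within six months. Every child who meets the count is taken to exit and asthma step-up is ignored, so these are upper limits.

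| Mean bursts per year | Children exiting | Of 80 |
|---|---|---|
| 0.3 | 0.18–0.85% | 0.14–0.68 |
| 0.5 | 0.81–1.90% | 0.65–1.52 |
| 1.0 | 4.09–5.44% | 3.3–4.4 |

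**5. Effect on the TNSS estimate.** Bias = (difference in loss between arms) × (TNSS gap between leavers and stayers). The standard error of the arm difference at 80 is 1.09 × √(4/80) = 0.244.
- Equal loss and equal gap in both arms: 0.
- 1.7% v 0%, gap 1 SD: 0.017 × 1.09 = 0.019.
- 5% v 2%, gap 1 SD: 0.03 × 1.09 = 0.033, or 0.13 SE.
- 5% v 0%, gap 2 SD: 0.05 × 2.18 = 0.109, or 0.45 SE.

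The loss rates and gaps are assumptions. The documents do not link burst count to TNSS, so the sign is unknown.

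**The case against.** The best defence is that SAP 6.1 promises disposition for all enrolled subjects and Protocol 13.4.6 promises it by arm, so the mITT heading may be template wording. The withdrawal bullets also follow a page break, so their place under that heading is the natural reading but not a certain one. This is fair, but the closing sentence on the listing is mITT only in plain terms, and no item in the section gives withdrawals by arm on a wider base. If all randomised children are meant, one phrase settles it.

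Some information would survive elsewhere. Arm sizes in mITT, set against 1:1 allocation, hint at unequal numbers lost. SAP 9.3 tabulates adverse events leading to stopping study drug in the safety sample, which may show some of these children. Physician decision, adverse event and other are available as rows. The content of the SAP 14.2 flow chart could not be read in the available text. So a reader might infer that attrition is hidden altogether, and the documents do not support that. What the planned table and listing cannot give is the reasons by arm.

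A reader might also infer that item 6 is itself a design flaw that biases the trial. That does not hold. Both 11.2.1 and 11.2.2 are permissive, 6.7 already lets the clinician stop injections alone, and 8.10 requires a face-to-face review after two exacerbations in a month. Protocol 5.2 names unstable asthma as a risk factor for fatal reactions. Many children with repeated bursts might also fail the asthma-control and washout conditions for the NAC in 8.1.5.

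Finally, the extracted SAP 14.3 schedule puts a NAC mark under Early Termination. The lavage and targeted-exam marks move with it, against Protocol 8.8, 8.9 and Appendix A, so it reads as a shifted column. An earlier challenge would not be the 12-month endpoint in any case.

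**Conclusion.** The point holds as a reporting defect in SAP 6.1. As written, early withdrawals counted by arm are zero by construction, and total withdrawals are near zero, whatever the true attrition. This contradicts the section's own opening and removes the direct check on differential loss in the complete-case analysis. It applies to every early leaver; item 6 is one example.

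The conclusion rests on the mITT definition and on reading the withdrawal bullets under the mITT heading. It does not depend on any assumed burst rate. Those rates bear only on item 6, where the likely numbers are small, power barely moves, and the largest scenario shown is under half a standard error with unknown direction. The documents show no actual bias in the primary estimate. Low priority, but very cheap to correct.

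**What to change.** **Before database lock, in SAP 6.1:**
- Give the number randomised, 12-month NAC completion, and withdrawals with reasons, by arm among all randomised children.
- Extend the disposition listing to all randomised children.
- Align the reason rows with Protocol 11.2.1 and 11.2.2, separating stopping therapy from ending participation, with a row for item 6.

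The cost is a changed denominator and a few rows. Protocol 11.3 already requires withdrawal reasons on the eCRF, and SAP 2 allows changes until lock.

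**Optional and secondary.** If children are still on study, when item 6 is met and it is safe, prefer stopping injections with continued follow-up (6.7, 11.4) to ending participation. Keep item 5 of 11.2.2, and attempt the 12-month NAC only if 8.1.5 is satisfied. Making this a rule would need an IRB-approved amendment (16.2) and a few extra visits, and it would recover the endpoint only in part. SAP 7.2 describes randomisation in the past tense, so it may reach few children.

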11.3 Participant Replacement

Participants who are discontinued prior to completing the study may be replaced as long as randomization for the study is still ongoing. All reasons for withdrawal will be captured on the appropriate electronic case report form (eCRF).

11.4 Follow-up after Study Therapy Discontinuation

Participants who discontinue study therapy after receiving one dose of investigational product will be asked to continue study follow-up for the remainder of the treatment period, using an altered visit schedule.

11.5 Study Stopping Rules

Study enrollment and treatment will be suspended pending expedited review of all pertinent data for the following reasons:

- 1) One death if at least possibly related to the investigational agent
- 2) Two Grade 4 systemic reactions possibly related to the injection of the investigational agent (see Table 12.3.1.1c)
- 3) One local Grade 4 reaction (see Table 12.3.1.1a) or Grade 4 systemic reaction (see Table 12.3.1.1c) possibly related to the NAC
 - a) The study will be halted for this occurrence pending review of pertinent data by DAIT/NIAID Medical Monitor (MM) and the NIAID Asthma and Allergy DSMB

If the study enrollment is stopped due to meeting the above criteria, it may not be resumed until all pertinent information is discussed with DAIT/NIAID, NIAID Asthma and Allergy DSMB, and the Central IRB, and all parties concur with the resumption of the study. The FDA will be notified if stopping rules are met and also on resumption of the study.

The study may be terminated by the IND sponsor (DAIT/NIAID) or the NIAID Allergy and Asthma DSMB upon review of any observations, events, or new information that merits such action.

12 Safety Monitoring and Reporting

12.1 Overview

This section defines the types of safety data that will be collected under this protocol and outlines the procedures for appropriately collecting, grading, recording, and reporting those data. Adverse events that are classified as serious according to the definition of health authorities must be reported promptly (per Section 12.5, Reporting of Serious Adverse Events and Adverse Events) to the IND sponsor (DAIT NIAID). Appropriate notifications will also be made to site Principal Investigators, Institutional Review Boards (IRBs), and appropriate Health Authorities.

Information in this section complies with ICH Guideline E2A: Clinical Safety Data Management: Definitions and Standards for Expedited Reporting, ICH Guideline E-6: Guideline for Good Clinical Practice, 21CFR Parts 312 and 320, and applies the standards set forth in the National Cancer Institute (NCI), Common Terminology Criteria for Adverse Events (CTCAE), Version [enter 4.0 or correct version applicable to trial] : <http://ctep.cancer.gov/reporting/ctc.html>.

12.2 Definitions

12.2.1 Adverse Event (AE)

Any untoward or unfavorable medical occurrence associated with the subject's participation in the research, whether or not considered related to the subject's participation in the research (modified from the definition of adverse events in the 1996 International Conference on Harmonisation E-6 Guidelines for Good Clinical Practice) (from OHRP "Guidance on Reviewing and Reporting Unanticipated Problems Involving Risks to Subjects or Others and Adverse Events (1/15/07)" <http://www.hhs.gov/ohrp/policy/advevntguid.html#Q2>)

The following are adverse events associated with study therapy and study procedures:

- **Study therapy regimen:** German cockroach allergenic extract administered by the subcutaneous route
 - Local Injection site reaction which requires a change in SCIT dose
 - Systemic reactions such as, but not limited to, those listed below:
 - Eye symptoms (itchy, runny, swelling)
 - Nose symptoms (sneezing, itching, runny, stuffy)
 - Mouth/ears/throat symptoms (itchy mouth, throat irritation, oral or throat angioedema, cough, itchy ears)
 - Skin symptoms other than local injection site reactions (angioedema, urticaria, generalized itching, rash)
 - Gastrointestinal symptoms (vomiting, diarrhea, cramps, nausea)
 - Chest (cough, tightness, wheezing)
 - Anaphylaxis (see Table 12.3.1.1b)
- **Study procedures:** AEs that occur due to a study procedure will be collected and recorded. The following clinical situations, when associated with study procedures, are defined as adverse events and will be recorded on the AE eCRF.

Blood Draws

- Fainting/Vasovagal events
- Bruising at puncture site larger than 2 cm diameter
- Bleeding from puncture site lasting more than 30 minutes
- Swelling at puncture site larger than 2 cm

Pulmonary Function Testing

- Wheezing or bronchoconstriction requiring treatment with bronchodilators within 30 minutes from the procedure

- Coughing requiring treatment with bronchodilators within 30 minutes from the procedure

Nasal Allergen Challenge

- Any clinical response requiring medication (see table 12.3.1.1a)

Allergen Skin Testing

- Prolonged (> 24 hours) itching at test site
- Swelling (> 10 cm) at site of test lasting more than 24 hours
- Nasal allergic symptoms within 30 minutes of the procedure
- Fainting/vasovagal event within 30 minutes of the procedure
- Anaphylaxis

12.2.2 Suspected Adverse Reaction (SAR)

Any adverse event for which there is a reasonable possibility that the investigational drug [or investigational study therapy regimen] caused the adverse event. For the purposes of safety reporting, 'reasonable possibility' means there is evidence to suggest a causal relationship between the drug and the adverse event. A suspected adverse reaction implies a lesser degree of certainty about causality than adverse reaction, which means any adverse event caused by a drug (21 CFR 312.32(a)).

12.2.3 Unexpected Adverse Event

An adverse event or suspected adverse reaction (SAR) is considered "unexpected" when its nature (specificity), or severity, or rate of occurrence is not consistent with the risk information described in the general investigational plan or elsewhere in the IND.

"Unexpected" also refers to adverse events or suspected adverse reactions that are mentioned in the package insert as occurring with a class of drugs or as anticipated from the pharmacological properties of the drug, but are not specifically mentioned as occurring with the particular drug under investigation (21 CFR 312.32(a)).

12.2.4 Serious Adverse Event (SAE)

An adverse event or suspected adverse reaction is considered "serious" if, in the view of either the investigator or the DAIT/NIAID Medical Monitor, it results in any of the following outcomes (21 CFR 312.32(a)):

1. Death.
2. A life-threatening event: An AE or SAR is considered "life-threatening" if, in the view of either the Principal Investigator or IND Sponsor, its occurrence places the subject at immediate risk of death. It does not include an AE or SAR that, had it occurred in a more severe form, might have caused death.
3. Inpatient hospitalization or prolongation of existing hospitalization.
4. Persistent or significant incapacity or substantial disruption of the ability to conduct normal life functions.
5. Congenital anomaly or birth defect.
6. Important medical events that may not result in death, be life-threatening, or require hospitalization may be considered serious when, based upon appropriate medical judgment,

they may jeopardize the subject and may require medical or surgical intervention to prevent one of the outcomes listed above.

Exacerbations of asthma are ordinary, anticipated complications of asthma observed in patients receiving standard of care. An asthma exacerbation that requires hospitalization and is determined to be a SAR (Section 12.2.1.1) will be considered a SAE. All other asthma hospitalizations will not be considered SAEs and will be entered only on the appropriate CRFs. The date of onset of the SAE will be the date of hospital admission and the date of resolution will be the discharge date. The underlying condition will be followed as per protocol.

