5.2 Risks of Investigational Product Cited in Medical Literature

In published studies of SCIT, systemic anaphylactic reactions with other inhalant allergens have been reported to occur in from 1% of patients to as many as 36% of patients receiving SCIT using a rush schedule.^{23,24} Protocol ICAC-28 does not involve a rush immunotherapy schedule. Fatalities are very rare but have been reported, as have specific risk factors for fatal reactions, which include unstable asthma, beta-blocker therapy, rush immunotherapy, and use of high doses of potent standardized extracts.²³ In our SCITCO study (Protocol ICAC-18), in 10 adults undergoing six months of SCIT, there were 2 serious adverse neither of which were considered related to the therapy.³

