12.5 Reporting of Serious Adverse Events and Adverse Events

12.5.1 Reporting of Serious Adverse Events to the IND Sponsor (DAIT/NIAID)

This section describes the responsibilities of the Principal Investigator to report serious adverse events to the IND sponsor via SAE eCRF. Timely reporting of adverse events is required by 21 CFR and ICH E6 guidelines.

Principal Investigators must report all serious adverse events (see Section 04, Serious Adverse Event), regardless of relationship or expectedness within 24 hours of becoming aware of the event.

For serious adverse events, all requested information on the AE/SAE eCRF will be provided. The following minimal criteria must be included in the initial SAE eCRF:

- AE Term
- Study Drug Treatment
- Relationship to study drug
- Reason why the event is serious

However, unavailable details of the event will not delay submission of the known information. As additional details become available, the AE/SAE eCRF will be updated and submitted. Every time the SAE eCRF is submitted, it should be electronically signed by the investigator or sub-investigator.

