12.5.2.2 Expedited Safety Reporting

This option, with 2 possible categories, applies if the adverse event is classified as one of the following:

Category 1: Serious and unexpected suspected adverse reaction [SUSAR] (see Section 12.2.2, Suspected Adverse Reaction (SAR), and Section 12.2.3, Unexpected Adverse Event and 21 CFR 312.32(c)(1)i).

The sponsor must report any suspected adverse reaction that is both serious and unexpected. The sponsor shall report an adverse event as a suspected adverse reaction only if there is evidence to suggest a causal relationship between the study drug and the adverse event, such as:

1. One or more occurrences of an event that is not commonly associated with drug exposure, but is otherwise uncommon in the population exposed to the drug (e.g., tendon rupture);
2. An aggregate analysis of specific events observed in a clinical trial (such as known consequences of the underlying disease or condition under investigation or other events that commonly occur in the study population independent of drug therapy) that indicates those events occur more frequently in the drug treatment group than in a concurrent or historical control group.

Category 2: Any findings from studies that suggests a significant human risk

The sponsor shall report any findings from other epidemiological studies, analyses of adverse events within the current study or pooled analysis across clinical studies or animal or *in vitro* testing (e.g. mutagenicity, teratogenicity, carcinogenicity) that suggest a significant risk in humans exposed to the drug that would result in a safety-related change in the protocol, informed consent, Investigator Brochure or Package Insert or other aspects of the overall conduct of the study.

DAIT NIAID must report to the FDA and notify all participating investigators of expedited Safety Reports within 15 calendar days; unexpected fatal or immediately life-threatening suspected adverse reaction(s) must be reported as soon as possible or within 7 calendar days.

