12.8.2 DSMB Review

12.8.2.1 Planned DSMB Reviews

NIAID Asthma and Allergy Data and Safety Monitoring Board (DSMB) shall review safety data at least yearly during planned DSMB Data Review Meetings. Data for the planned safety reviews will include, at a minimum, a listing of all reported AEs and SAEs.

The NIAID Asthma and Allergy DSMB will be informed of an Expedited Safety Report as determined by the DAIT NIAID Medical Monitor. An SAE which the DAIT NIAID Medical Monitor determines to be an unexpected safety risk will be sent to the DSMB immediately.

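### Asthma hospitalisations judged unrelated are not SAEs, with no stated exception for death or life-threatening events, and no by-arm count of them is planned for the DSMB or the SAP safety tables

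*Protocol*

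**What the plan says.** Protocol 12.2.4 lists six outcomes, any one of which makes an event serious. Item 1 is death. Item 2 is a life-threatening event, meaning that "its occurrence places the subject at immediate risk of death". Item 3 is "Inpatient hospitalization or prolongation of existing hospitalization". After the list, the section describes exacerbations as an expected part of asthma and sets a special rule: "An asthma exacerbation that requires hospitalization and is determined to be a SAR (Section 12.2.1.1) will be considered a SAE". The next sentence is "All other asthma hospitalizations will not be considered SAEs and will be entered only on the appropriate CRFs".

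Four other parts of the plan depend on that definition:

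- **Reporting to the sponsor (Protocol 12.5.1).** SAEs are reported "regardless of relationship or expectedness within 24 hours of becoming aware of the event".
- **Medical monitor (Protocol 12.8.1).** The monthly report compiles major deviations, AEs, SAEs and pregnancies.
- **DSMB (Protocol 12.8.2.1).** The minimum content is "a listing of all reported AEs and SAEs". SAP section 11 adds discontinuations of treatment.
- **Final safety output (SAP 9.3 and 9.4).** AEs, SARs, AEs leading to discontinuation, SAEs and deaths are listed and summarised.

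**The concern.** Seriousness normally describes the outcome of an event, and relatedness is judged separately. Here relatedness decides seriousness for one class of event. A site with a child ventilated for asthma that is judged unrelated to the injections has two instructions: item 2 says serious, and the later sentence says not an SAE.

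The event class matters in this trial. Allergen is injected into children with persistent asthma. Protocol 5.1 lists chest tightness and wheezing among the risks of immunotherapy. Protocol 5.2 gives risk factors for fatal reactions, "which include unstable asthma, beta-blocker therapy, rush immunotherapy" among them. Worsening asthma is therefore both the background disease and a plausible drug effect. Single cases of that kind are hard to attribute. Protocol 12.5.2.2 recognises this: for events common in the study population it relies on an aggregate analysis that "indicates those events occur more frequently in the drug treatment group than in a concurrent or historical control group". That comparison needs a complete count by arm, and the plan does not clearly provide one.

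**Working it through.** The documents give no figure for asthma admissions, so there is no stated result to reproduce. The check compares the passages and adds one timing calculation.

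**1. Which rule governs.** Items 1, 2 and 3 of Protocol 12.2.4 carry no condition on causality. The later sentence covers all asthma hospitalisations other than SARs, with no exception. Read literally, it displaces item 3 and also reaches items 1 and 2 when the child was admitted. Read narrowly, it qualifies item 3 alone. The text does not say which reading is meant.

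**2. What decides SAR status.** Under Protocol 12.3.2 the study clinician attributes first and the sponsor decides finally. The possible category counts as related, while the unrelated category includes cases where evidence of causality is insufficient. The carve-out cites section 12.2.1.1 for the SAR definition, but that definition is in 12.2.2. SAP 9.1 and 9.3 repeat the wrong number.

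**3. What 24-hour reporting catches.** Protocol 12.5.1 disregards relationship, but only for SAEs. An admission removed from the SAE definition is not covered.

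**4. Whether AE recording catches it.** Protocol 12.4.3 records AEs whatever the relationship, and 12.3.1.2 sends events of Grade 1 or higher to the AE form. Against that, 12.4.3 refers back to section 12.2, which contains the carve-out, and the carve-out says *only*. Protocol 8.1.8 also lists exacerbation history and health care use separately from AE information. The answer depends on whether the appropriate CRFs include the AE form, and the protocol does not say.

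**5. What the DSMB and the safety tables show.** Protocol 12.8.2.1 and SAP 9.3 and 9.4 name AEs, SARs, SAEs, discontinuations and deaths. None names asthma hospitalisations or exacerbations.

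**6. Whether the exploratory analysis fills the gap.** Protocol 7.4.1 defines an exacerbation to include hospitalisation, with no causality filter. SAP 8.4.3 compares exacerbations by arm using the CASI model, which SAP 8.4.1 describes for the 10- and 12-month assessments.

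- *Look-back.* E&M visits are two months apart, and Table 7.1.1.2a counts steroid courses since the last such visit. Assume the endpoint uses the same look-back.
- *Window.* The 10-month assessment then reaches back to month 10 − 2 = 8, which is 8 × 52/12 ≈ 35 weeks. The model covers roughly week 35 to week 52.
- *Escalation.* Appendix A gives 16 to 26 weeks as usual and 40 as the limit. Usual escalation ends at least 35 − 26 = 9 weeks before the window opens. The slowest escalation overlaps it by about 40 − 35 = 5 weeks. COVID-19 resets under Appendix B could lengthen this for some children.

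Protocol 11.2.2 also allows a child with repeated steroid bursts to be terminated from the study, so some of the worst affected may have left by month 10. In any case this is an end-of-study efficacy analysis and does nothing for monitoring during the trial.

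**The case against.** The carve-out is deliberate and explained: exacerbations are expected in this population, and expediting each admission would add noise. Participants must be well controlled at entry and free of recent asthma admissions. Attribution does not rest with a blinded clinician alone, because the sponsor decides finally. Post-injection asthma is graded as a systemic reaction, and delayed reactions are asked about at each visit. If these admissions are recorded as AEs, they reach the DSMB listing, the monitor's report and the SAP tables by arm. The DSMB content is only a minimum, and ad hoc review is open to any event affecting safety. The exacerbation model is not the only by-arm asthma display, since SAP 8.4.1 also summarises CASI by arm at each visit after the first injection.

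Much of this stands. It does not supply the missing pieces. CASI summaries are not admission counts, AE capture is unclear, and no safeguard promises the DSMB a complete count.

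Three stronger inferences are tempting and should be resisted:

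- *A fatal or life-threatening asthma admission would disappear.* Items 1 and 2 stand as separate criteria, so this is an unresolved conflict, not an established override. SAP 9.4 displays deaths and their causes without a relatedness filter. Life-threatening events that the child survives have no equivalent display.
- *Asthma admission is the main harm the protocol names.* It is not. Protocol 5.1 expects mainly local swelling where the injection was given, and 5.2 centres on systemic anaphylactic reactions.
- *An excess of some particular size would be hidden.* The documents give no admission rate, so any such count would be invented.

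**Conclusion.** The point holds as a gap in definition and reporting. Protocol 12.2.4 contradicts its own seriousness items and lacks an explicit exception for fatal and life-threatening asthma events. Admissions judged unrelated escape 24-hour SAE reporting as written, and they may escape the AE and SAE listings too. No by-arm count of them is specified for the DSMB or SAP section 9, and the exploratory model largely misses escalation.

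No number of affected events can be given. With 80 children randomised 1:1, or 80/2 = 40 per arm, counts would probably be too small for a useful test, so a complete listing by arm is what matters. The conclusion that the model misses escalation assumes a two-month look-back at each assessment. Whether these admissions drop out of the AE listings depends on which forms the protocol means. The change should be made, but the documents do not show that a safety signal would be lost.

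**What to change.** 1. **Protocol 12.2.4.** State that an asthma event meeting item 1 (death) or item 2 (life-threatening) is an SAE whatever its attribution, so that the carve-out is an exception to item 3 only. Say whether the appropriate CRFs include the AE form. Correct the SAR cross-reference from 12.2.1.1 to 12.2.2, here and in SAP 9.1 and 9.3.
2. **Protocol 12.8.2.1 and SAP 9.4.** List and tabulate all asthma hospitalisations and all systemic-steroid exacerbations from first injection, whatever the attribution, by arm and by phase (escalation, maintenance). During the trial, by-arm output goes to the DSMB only.
3. **Protocol 12.8.1.** Include the same events in the medical monitor's monthly reports, pooled across arms. By-arm figures there would threaten the blind that Protocol 3.5 protects.

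The cost is a few sentences, slightly more SAE reports and one more table. The data are already collected, and no treatment or visit changes.
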